#### 6.3 Statistical Methods

[figure not shown]
For analysis, each CPR event will be divided into multiple 30-second epochs. An average of the following will be calculated: 1) ventilation rate (bpm); 2) ETCO2 (mmHg); 3) compression rate; 4) arterial BPs; 5) chest compression fraction; 6) compression depth (mm); 7) exhaled tidal volume (mL); 8) minute ventilation (L/minute); 9) PIP (cm H2O); 10) PEEP (cm H2O); 11) % leak; and 12) cerebral oxygen saturation. An average of all epochs (event-level average) will be used in survival analyses.

#### Primary Objective (Efficacy of OPTI-VENT bundle)

The analysis of our primary outcome is based on all enrolled index events (first in-ICU cardiac arrest) excluding transition periods. For the primary analysis of the interventional trial, a mixed effect logistic regression model will be fit with our primary outcome as the dependent variable. The primary predictor will be treatment group, an indicator of whether the *OPTI-VENT* bundle was fully implemented prior to the arrest. Fixed covariates will be illness category, age, first documented rhythm, and time since trial start (to prevent confounding due to unrelated temporal changes in outcome). Etiology and severity of pre-existing lung disease will be evaluated as a confounder / effect modifier. Unit will be included as a random effect to account for heterogeneity in patient outcomes across ICUs and to accommodate clustering of patients within ICUs. The null hypothesis will be tested using the standard type III test for the fixed effect, and the p-value for the two-sided alternative will be presented.

Brief Description of Secondary Analytic Objectives

Ventilation Rate and Survival: We will explore the relationship between ventilation rate and survival using cubic splines and ROC curves. We will randomly divide our cohort into a derivation set (70%) and a validation set (30%). The derivation set will be used in an exploratory fashion to identify an optimal target using cubic splines and ROC curves in conjunction with clinical expertise. Then, the validation set will be used to validate the rate selected and to provide an unbiased estimate of the effect of achieving the target rate on outcome. Cubic splines will allow us to create a smooth curve of survival probability on the vertical axis against the event-level average ventilation rate on the horizontal axis, while controlling for potential confounders. We plan to stratify our analysis by age,

**Figure 2:** Airway Opening Index. The sum of the delta in ETCO2 divided by the max ETCO2 caused by each chest compression is averaged by the number of CCs. Higher values indicate greater airway patency.

and either adjust for / stratify by initial rhythm, immediate cause of arrest (e.g., respiratory deterioration, shock, sudden arrhythmia), severity (none, non-severe, severe) and etiology (none, obstructive, restrictive, mixed) of pre-existing lung disease, chest compression depth and rate (AHA compliant vs. not), and clinical site. If an alternative ventilation rate target is identified, we will quantify its association with survival outcomes using logistic regression models. Similarly, we will also explore the relationship between ventilation rate and 1) arterial diastolic BP and 2) exhaled carbon dioxide using linear regression models. For this analysis, individual epoch data will be used. Models will be adjusted for the same variables as above and account for the clustering of epochs from within events.

Evaluation of Airway Opening Index: The calculation of Airway Opening Index will be done in the manner as described in Grieco et.al. (Figure 2). As with other variables, an average AOI for each 30-second CPR epoch will be calculated. For each event, the average of all the epochs will be calculated to be used in logistic regression survival analyses. Epoch-level data will be used in a similar fashion as described above to evaluate the association of AOI with intra-arrest physiology (e.g., blood pressure and ETCO2) and delivered airway pressures (e.g., positive end expiratory pressure) in linear regression models, accounting for the clustering of epochs from within events. In addition to these standard statistical methods, this exploratory aim will involve the development of a multi-modal ML model. The input data will comprise both discrete values (e.g., demographic and clinical variables, ETCO2, I/E ratio) and high-fidelity waveform data (e.g., arterial BP, capnogram). To evaluate model performance, we will use metrics such as accuracy, F1-score, and AUC-ROC.

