## **Number Of Subjects**

Total Number of Subjects: 1530

Total Number at CHOP: 200 (estimated)

Total Number of Sites: 20

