
_	
Efficacy Evaluations	The primary outcome is survival to hospital discharge with favorable neurologic outcome, defined as a PCPC score of 1-2 or no change from baseline.
Pharmacokinetic Evaluations	NA
Safety Evaluations	NA
Statistical And Analytic Plan	The analysis of survival to discharge with favorable neurological outcome is based on all enrolled index events excluding transition periods. For the primary analysis, a mixed effect logistic regression model will be fit with our primary outcome as the dependent variable. The primary predictor will be treatment group, an indicator of whether the OPTI-VENT bundle was fully implemented prior to the arrest. Fixed covariates will be illness category (e.g., medical cardiac, medical non-cardiac, surgical cardiac), age, first documented rhythm, and time since trial start (to prevent confounding due to unrelated temporal changes in outcome). Etiology and severity of pre-existing lung disease will be evaluated as a confounder / effect modifier. Unit will be included as a random effect to account for heterogeneity in patient outcomes across ICUs and to accommodate clustering of patients within ICUs. The null hypothesis will be tested using the standard type III test for the fixed effect, and the p-value for the two-sided alternative will be presented.

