## 3.2 Allocation to Treatment Groups and Blinding

The basis of this investigation is a hybrid between a parallel and stepped-wedge cluster-randomized trial (13). As in a parallel design, 5 randomly selected sites will be permanently assigned to enroll in the control group, and 5 others will be permanently assigned to enroll in the intervention group. The remaining 10 sites, as in a stepped-wedge design, will initially enroll in the control group but will be randomly assigned a time to begin implementing the intervention. Data collection will be continuous for the entire 4.25-year study, but events enrolled in the 8-week transition period after the intervention is initiated will be excluded from analyses comparing intervention to control. In order to ensure roughly equal numbers of subjects in the intervention and control groups, and to ensure balance with respect to baseline pre-trial survival rates, the computer-generated randomization schedule will be selected from all possible configurations with sufficient expected balance in both expected enrollment and pre-trial survival rates.

[figure not shown]

Figure 1: Schematic summary of overall study design

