## 6.4 Sample Size and Power

Primary Objective (Efficacy of OPTI-VENT bundle)

Based on pediRES-Q data, ~360 index CPR events are expected to occur annually. After excluding ~7 events/year that occur during transition periods, 1500 index events will be available for analysis. In our preliminary work, rates consistent with 2020 AHA Guidelines were associated with

	Compliance with Ventilation Rate Target (20 – 30 bpm)			
Absolute improvement in survival with favorable neurologic outcome	85%	90%	95%	
12%	70%	76%	82%	
14%	82%	87%	91%	
16%	91%	94%	97%	

an improvement in survival with favorable neurologic outcome of >20 percentage points. Understanding that it is likely that the magnitude of the effect will be smaller in a multicenter study, we have provided estimated power to detect a 12-16% improvement when

the target rate is achieved compared to a baseline rate of survival with favorable neurologic outcome of 30% (data obtained from an existing pediRES-Q online real-time dashboard) when the target rate is not achieved. We also show the impact of the level of compliance with the target rate that we can achieve in the intervention group compared to a control group rate of 20%. We have assumed an intra-cluster correlation of 2% (based on our prior IHCA data). To ensure adequate power, we have included a pre-planned adaptive design. If after 12 months of enrollment, sites are enrolling ≤90% of expected, we will add 6 additional ICUs. If they are enrolling ≤75% of expected, we will add an additional 10 ICUs. As the pediRES-Q network has more than 50 active domestic / international sites, recruiting 10 sites is feasible. New sites if added will all begin in the control group starting at 14 months and will randomly be assigned a transition time according to a standard stepped-wedge design. Start-up within 2 months is feasible due to these sites starting in control, our plan for continuous enrollment monitoring, and the infrastructure of the pediRES-Q network (active IRBs and DUAs). Our design adaptation can also be used to mitigate power issues due to unexpectedly high baseline compliance in the control group or inability to achieve compliance training targets in the interventional group.

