#### 9 STUDY ADMINISTRATION

#### 9.1 Treatment Assignment Methods

#### 9.1.1 Randomization

The basis of this investigation is a hybrid between a parallel and stepped-wedge cluster-randomized trial. As in a parallel design, 5 randomly selected sites will be permanently assigned to enroll in the control group, and 5 others will be permanently assigned to enroll in the intervention

group. The remaining 10 sites, as in a stepped-wedge design, will initially enroll in the control group but will be randomly assigned a time to begin implementing the intervention. In order to ensure roughly equal numbers of subjects in the intervention and control groups, and to ensure balance with respect to baseline pre-trial survival rates, the computer-generated randomization schedule will be selected from all possible configurations with sufficient expected balance in both expected enrollment and pre-trial survival rates.

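### The schedule is constrained on site pre-trial survival rate but the primary model omits that rate: valid, but it forgoes a small gain in power if the rate is prognostic

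*Protocol*

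**What the plan says.** Section 3.2 restricts the allocation: "to ensure balance with respect to baseline pre-trial survival rates, the computer-generated randomization schedule will be selected from all possible configurations" that meet the balance requirement. Section 9.1.1 repeats this, requiring "sufficient expected balance in both expected enrollment and pre-trial survival rates". Neither section says how tight the balance must be.

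Section 6.3 (Primary Objective) specifies a mixed-effects logistic model with unit as a random effect and a standard type III test of treatment. Its covariate sentence reads "Fixed covariates will be illness category, age, first documented rhythm, and time since trial start". The synopsis (Statistical and Analytic Plan) gives the same list, ending "surgical cardiac), age, first documented rhythm, and time since trial start". The only item left open is pre-existing lung disease, to be examined as a confounder or effect modifier. Nothing in the protocol brings the pre-trial rate into the analysis or plans a randomisation test over the admissible schedules. No statistical analysis plan was available.

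Section 6.4 provides for extra ICUs if enrolment lags: "New sites if added will all begin in the control group starting at 14 months". It does not place them under the balance constraint.

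**The concern.** Balancing on a site characteristic that predicts outcome reduces the true variance of the treatment estimate. A model without that characteristic cannot see the reduction. Its random unit effect treats all between-site variance as free to fall unevenly between arms, so the reported standard error exceeds what the constrained design delivers, before any small-sample effect. At stake is some power, in a trial whose own table gives 70% and 76% at a 12-point improvement with 85% and 90% compliance. The trial must hold the pre-trial rate for every original site in order to randomise, and this choice has to be made before outcomes are seen.

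**Working it through.** **Inputs from the protocol.** 5 control, 5 intervention and 10 stepped-wedge sites; 4.25 years (51 months); 8-week transitions excluded (Section 3.2). Baseline 30%, control compliance 20%, intra-cluster correlation (ICC) 2% (Section 6.4). Two-sided alpha 0.05 (Section 6.5). About 200 subjects expected at one site (synopsis).

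**The plan's own figures.** N: 4.25 × (360 − 7) = 1500. A generalised least squares (GLS) variance for the hybrid design, with site random intercept, control risk 0.30 + 0.20 × effect, intervention risk 0.30 + compliance × effect and no time term, gives 69.5/75.6/81.1, 81.7/86.8/90.9 and 90.2/93.8/96.3%. The protocol has 70/76/82, 82/87/91 and 91/94/97%, so every cell agrees within 1 point. The calculations below include a linear time term, because the primary model has one. Their base power is therefore lower than the table's, which is a separate matter from the omitted rate.

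**Assumptions.** One unit per site; five steps of two sites. R², the share of between-site variance explained by the pre-trial rate, is not in the protocol; 0.10, 0.27 and 0.52 are used. The last two follow from n × 0.02 / (1 + (n − 1) × 0.02) with 360/20 = 18 events per site-year: n = 18 gives 0.36/1.34 = 0.27, and n = 54 gives 1.08/2.06 = 0.52. Sufficient balance is taken as a draw from the best 10 of 50 allocations on pre-trial survival.

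**Known variances (GLS), 12 points at 90% compliance.** Effect = 0.12 × (0.90 − 0.20) = 0.084; risks 0.324 and 0.408, mean 0.366.

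- Null size = 2Φ(−1.96 × reported SE / true SE)
- Power = Φ((0.084 − 1.96 × reported SE) / true SE)
- Size-matched power uses the true SE in both places.

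| R² | Reported SE, unadjusted | True SE, unadjusted | True SE, adjusted | Null size, unadjusted | Power, unadjusted → adjusted | Size-matched |
|---|---|---|---|---|---|---|
| 0.10 | 0.0349 | 0.0344 | 0.0344 | 4.7% | 67.4 → 68.5 | 68.5 → 68.5 |
| 0.27 | 0.0349 | 0.0335 | 0.0334 | 4.1% | 67.8 → 71.1 | 70.6 → 71.1 |
| 0.52 | 0.0349 | 0.0322 | 0.0316 | 3.4% | 68.5 → 75.8 | 74.1 → 75.8 |

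Example at R² 0.27: 1.96 × 0.0349/0.0335 = 2.042, two-sided tail 4.1%. At R² = 0 power is 67.2 → 67.2. The constraint itself supplies nearly all the precision: the two true SEs barely differ.

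**Estimated variances.** Logistic mixed model (Laplace), one site of 200 and 19 of 70, 6,000 trials per R² and hypothesis; t with 18 df unadjusted and 17 adjusted.

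| R² | Actual spread of log OR, unadj. / adj. | Mean model SE, unadj. / adj. | Null size, normal, unadj. | Null size, t, unadj. / adj. | Power, t, unadj. → adj. | Size-matched difference |
|---|---|---|---|---|---|---|
| 0.10 | 0.154 / 0.155 | 0.147 / 0.143 | 6.2% | 4.7 / 5.4% | 63.0 → 64.8 | −0.9 |
| 0.27 | 0.150 / 0.150 | 0.147 / 0.138 | 5.8% | 4.5 / 5.9% | 62.7 → 67.3 | −0.5 |
| 0.52 | 0.145 / 0.142 | 0.148 / 0.132 | 4.7% | 3.3 / 5.8% | 63.3 → 72.8 | +0.7 |

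The size-matched differences have Monte Carlo SE 0.6 to 0.8. With a normal reference the adjusted test rejects 7.1 to 7.6% under the null.

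**Sensitivity.** Size-matched GLS gains at the three R² values are 0.0/0.4/1.5 for the best 1 of 50, 0.1/0.5/1.7 for the best 10 and 0.1/0.8/2.6 for the best 25. Ranking on survival and enrolment together, with one site of 200, gives 0.2/1.1/3.2; the matching simulation (8,000 trials) gives −0.5/+0.5/+3.1, with adjusted t size 5.0 to 5.4%. A second logistic simulation with equal expected site sizes, correlations 0.3/0.6/0.9 between rate and site effect and the tightest 10% of allocations gives t sizes of 4.4/3.3/1.8% without the rate and 5.4/5.0/4.1% with it. Its normal-reference sizes without the rate are 5.7/4.2/3.1%, against 6.3 to 7.7% under unconstrained randomisation.

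**The case against.** The strongest reply has four parts.

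- **The test is not simply conservative.** Section 6.3 names no reference distribution. With a normal one, the simulated size is above 5% at the two lower R² values. This stands: a reader might infer that the stated test always rejects below 5%, but that holds only with a cluster-based reference or a strongly prognostic rate. What holds more generally is the comparison with unconstrained randomisation.
- **The covariate does not by itself make the reported standard error right.** This also stands. In the simulation the unadjusted SE differs from the actual spread by about −5, −2 and +2%; the adjusted SE falls short by about 8, 8 and 7%. With t, adjusted sizes of 5.9 and 5.8% exceed 5% by more than the Monte Carlo error of about 0.28 points. A small-sample correction is needed with the covariate, and how well it calibrates depends on how the constraint is applied.
- **The gain is close to zero at equal size, and R² may be low.** This stands too. The balancing rate is described only as survival, not survival with favourable neurologic outcome, and illness category, age and rhythm may already explain part of the site differences.
- **It is only a preference about covariates, or a matter for the analysis plan.** This does not fully stand. The protocol states its covariate list twice and leaves out the variable by which it restricts randomisation. That is a stated choice, and it can be improved cheaply.

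**Conclusion.** The mismatch between design and analysis is real, but its consequence is minor. A reader might infer bias, inflated type I error or a wrong power table. None follows: the constraint and the omission leave the estimate unbiased, the omission lowers the rejection rate, and the table reproduces without any reference to the rate.

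What is lost depends on how prognostic the rate is. With known variances, null size is 4.7/4.1/3.4% at R² 0.10/0.27/0.52; with estimated variances and a normal reference, small-sample inflation can hide this. Adding the rate raises simulated power on the same t reference by 1.8, 4.6 and 9.5 points, almost all of it recovered test size. Size-matched, the gain is about 0 to 2 points; values clearly above 2 arise only at R² 0.52 with a looser or two-criterion constraint. It is nil at R² = 0. These figures rest on an assumed R², tightness of balance, step pattern and site sizes, none of which the protocol quantifies. The change is worthwhile because it is cheap, but it is not essential.

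**What to change.** In Section 6.3 and the synopsis, add the site pre-trial survival rate used in the constraint as a prespecified fixed site-level covariate, and state that treatment is tested with cluster-based (small-sample) degrees of freedom for about 20 clusters. The exact form of the correction can be left to the statistical analysis plan. Record the same pre-trial figure for any site added at 14 months, so that those sites are not lost from the adjusted model.

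Cost: one sentence in each place, one cluster-level degree of freedom and one figure per added site. Adjusted t-test size was about 5.0 to 5.9% in the simulations with one large site. The small-sample correction lowers nominal power by about 5 points with or without the covariate (unadjusted: 68.2 → 63.0, 67.8 → 62.7, 68.8 → 63.3). So the covariate and correction together, set against an unadjusted normal-reference test, give 64.8 vs 68.2, 67.3 vs 67.8 and 72.8 vs 68.8 at R² 0.10/0.27/0.52. In the first two, the comparator is itself oversized (6.2 and 5.8%). The covariate should not be added without the correction.

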## 3.3.2 Total Number of Study Sites/Total Number of Subjects Projected

The study will be conducted at approximately 20 investigative sites in the United States.

Recruitment will stop when approximately 1530 subjects are enrolled. As per the study design, enrollment will end 4.25 years from study start.

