#### 4 STUDY PROCEDURES

Standard cardiac arrest data (e.g., demographics, intra- and post-arrest physiologic variables, CPR quality variables) will be collected on all subjects, extracted from the electronic medical record, continuous bedside monitors, and other patient physiologic monitoring devices (e.g., NIRS). Data elements to be collected from the pre-, intra-, and post-arrest periods include but are not limited to:

Patient Characteristics: date of birth; sex; race/ethnicity; height; weight; illness category (medical cardiac, medical non-cardiac, surgical cardiac, surgical non-cardiac, trauma). Pre-existing conditions: respiratory insufficiency; hypotension; congestive heart failure; pneumonia; sepsis; trauma; renal insufficiency; malignancy; congenital heart disease, if yes, single ventricle; if single ventricle, the anatomy is specified; if surgical palliation completed, type of most recent surgical procedure is noted (Norwood with Sano modification, Norwood with modified BT shunt, Hybrid Procedure, Bi-directional Glenn, Fontan, other); vasoactive inotropic scores (2 hours preceding CPR); pediatric cerebral performance category (PCPC) score; functional status scale (FSS) score.

CPR Event Characteristics: interventions at CPR start (e.g., vasoactive infusion); immediate cause of arrest (Y/N for hypotension, respiratory decompensation, arrhythmia, cyanosis without respiratory decompensation); first documented rhythm requiring CPR; time of first shockable rhythm; pre-shock pause (seconds); time of first defibrillation; time of first vasopressor administration for non-shockable rhythm; drug interventions during CPR; duration of CPR (minutes). CPR mechanics variables: Compression depth (mm); rate (per minute); chest compression fraction; and leaning during relaxation phase (release velocity, if available [mm/second]). Ventilation variables: ETCO2 (mmHg); ventilation rate (bpm); airway opening index; other ventilation variables as available (e.g., Peak Inspiratory Pressure [cmH2O]). Intra-arrest physiology (arterial BP (mmHg), ETCO2 (mmHg), and arterial/venous blood gases.

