# **6 STATISTICAL CONSIDERATIONS**

# 6.1 Primary Endpoint

The primary outcome is survival to hospital discharge with favorable neurologic outcome, defined as a PCPC score of 1-2 or no change from baseline. Baseline will be defined as the child's pre-

admission status. For those children hospitalized more than 90 days at the time of their CPR event, a new "baseline" will be assessed at least 30 days prior to the CPR event.

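### The primary model omits baseline PCPC, which is collected, precedes the arrest and sets the criterion each child must meet to count as favorable

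*Protocol*

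**What the plan says.** The covariate list is in protocol section 6.3 under the primary objective: "Fixed covariates will be illness category, age, first documented rhythm, and time since trial start". One further candidate is left open: "Etiology and severity of pre-existing lung disease will be evaluated as a confounder / effect modifier". Clustering is handled by a random intercept: "Unit will be included as a random effect to account for heterogeneity in patient outcomes across ICUs". The synopsis gives the same model.

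Section 4 lists, among patient characteristics, "vasoactive inotropic scores (2 hours preceding CPR); pediatric cerebral performance category (PCPC) score; functional status scale (FSS) score". Section 6.1 makes PCPC the basis of the endpoint, with favorable survival "defined as a PCPC score of 1-2 or no change from baseline". Baseline is pre-admission status. For children already in hospital for more than 90 days, a new baseline "will be assessed at least 30 days prior to the CPR event".

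On design, "The study will be conducted at approximately 20 investigative sites in the United States". Under section 3.2, five sites stay in control throughout, five deliver the bundle throughout, and the other ten cross from control to intervention. Sections 3.2 and 9.1.1 restrict the randomization schedule to configurations balanced on expected enrollment and pre-trial survival.

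**The concern.** Baseline PCPC decides which test a child has to pass, so its link to the outcome follows from the endpoint definition and needs no outside evidence. It is recorded from before the admission, or at least 30 days before the arrest, so neither the resuscitation nor the training bundle can change it. The listed covariates cover type of illness, age, rhythm and calendar time; none describes neurologic status before the arrest.

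Two things are at stake. The first is some power, in a trial whose own table has cells below 80%. The second is exposure to chance differences between sites in the share of children with prior neurologic disability. That exposure is greatest in the parallel part, where five sites are compared with five others and no site serves as its own control.

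**Working it through.** **1. The endpoint by baseline status (section 6.1)**

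| Baseline PCPC | Discharge PCPC that counts as favorable |
|---|---|
| 1 or 2 | 1 or 2 |
| 3, 4 or 5 | 1 or 2, or the same score as at baseline |

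A survivor with baseline 5 who is unchanged is favorable, so for that child the endpoint is close to survival alone.

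**2. Reproducing the power table (section 6.4)**

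Inputs from the protocol: 1500 analysable events (353 × 4.25 ≈ 1500); 30% favorable when the target rate is missed; gains of 12, 14 or 16 points when it is met; compliance of 85, 90 or 95% against 20% in control; ICC 0.02; two-sided alpha 0.05; 5 control, 5 intervention and 10 stepped sites over 51 months, with transition periods excluded. Assumptions: ten evenly spaced step dates (the schematic is not shown), a two-month transition, and events spread evenly over sites and months.

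- Arm rates for 12 points and 90% compliance: control 0.30 + 0.20 × 0.12 = 0.324; intervention 0.30 + 0.90 × 0.12 = 0.408; difference 0.084.
- Mean rate 0.366; binary variance 0.366 × 0.634 = 0.2320.
- Ignoring clusters: SE = √(0.2320 × 2/750) = 0.0249; power = Φ(0.084/0.0249 − 1.96) ≈ 92%.
- Generalized least squares for the hybrid design with a random cluster intercept and no time term: 75.4%, against 76% stated.
- All nine cells: 69.3/75.4/80.9, 81.5/86.7/90.7 and 90.1/93.7/96.2, against 70/76/82, 82/87/91 and 91/94/97 stated. The largest gap is 1.1 points.
- With the time term that section 6.3 requires, the 76% cell becomes 67.7% and no cell matches. That is a separate matter, but both versions are carried below.

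**3. Adding prognostic covariates**

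Split the variance into a between-ICU part, 0.02 × 0.2320 = 0.0046, and a within-ICU part, 0.98 × 0.2320 = 0.2274. A covariate that explains a share R² of the within-ICU part replaces 0.2274 by 0.2274 × (1 − R²). R² here means variance explained beyond the covariates already listed. The documents give no value, so the range is assumed.

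| R² | 12 points/90%, no time term | 12 points/90%, time term | 14 points/90%, no time term | 14 points/90%, time term |
|---|---|---|---|---|
| 0 | 75.4% | 67.7% | 86.7% | 80.1% |
| 2% | 76.1% | 68.3% | 87.2% | 80.7% |
| 5% | 77.0% | 69.3% | 87.9% | 81.5% |
| 10% | 78.6% | 70.9% | 89.1% | 82.9% |

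In the 12-point, 90% cell, R² of 2-10% adds 0.7 to 3.2 points without the time term and 0.6 to 3.2 with it. If the covariates also removed a quarter of the between-ICU variance, the cell without the time term would reach 79.1% (R² 2%) to 81.5% (R² 10%), a gain of 3.7 to 6.1 points.

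**4. What happens on the logistic scale**

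Simulation with 1500 children, no clustering, arm rates of about 32.4% and 40.8%, and one standardized prognostic covariate. Each cell shows unadjusted, then adjusted.

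| Covariate log odds per SD | Treatment log OR | Its SE | Power |
|---|---|---|---|
| 0.3 | 0.368, 0.376 | 0.108, 0.109 | 93.3%, 93.5% |
| 0.5 | 0.359, 0.381 | 0.108, 0.111 | 91.9%, 93.5% |
| 0.8 | 0.356, 0.405 | 0.108, 0.115 | 92.2%, 94.3% |

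Adjustment raises the standard error slightly and moves the conditional estimate further from zero. The net effect is a power gain of 0.2 to 2.1 points.

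**The case against.** The strongest reply is that this is a preference among covariates. The plan already names three patient-level prognostic factors, time, a unit effect and an evaluation of lung disease. Other variables in section 4 could be proposed just as well, and no figure in the protocol becomes false. The statistical analysis plan, which is not at hand, may add adjustment. The endpoint itself already takes account of baseline, so the prognostic signal left over is unknown in size and direction. Imbalance is also partly handled, by restricted randomization on pre-trial survival, ten sites with within-site comparisons, and the random effect.

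Much of this stands: the omission is neither an error nor a contradiction, and the size is uncertain. It does not dispose of the point. The protocol itself names the list, and the missing variable is the one that sets the success criterion. The randomization constraint is at site level, historical and about survival. It does not balance the neurologic status of the children enrolled, and section 6.4 states no such constraint for ICUs added later.

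Four stronger readings are tempting, and the documents do not support them.

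- **Free precision.** In logistic regression the standard error of the treatment effect rises; the gain is in power.
- **A large gain.** Scaling all the variance by 1 − R² would take 76% to 80.2% at R² of 10%, because Φ((1.96 + 0.706)/√0.9 − 1.96) = 0.802. That also shrinks the between-ICU part, which a patient-level covariate need not touch.
- **A biased primary estimate.** What remains is chance imbalance in a randomized comparison, and the unit effect absorbs part of it.
- **The vasoactive score as an equal omission.** It is measured after cluster assignment, in units running a bedside training program, and it may be missing.

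**Conclusion.** The point holds for baseline PCPC as a worthwhile improvement to the prespecified primary model. The benefit is modest: about 0.6 to 3 points of power in the 12-point, 90% cell under an assumed R² of 2-10%, and roughly 4 to 6 points (no time term) if a quarter of the between-ICU variance were also explained. Neither assumption can be checked from the documents. The figures also rest on assumed step dates and on a normal approximation with rates on the linear scale; the unclustered logistic simulation gives gains of similar size. The second benefit, protection against chance case-mix differences in the 5 versus 5 parallel sites, is real but cannot be quantified here. The omission does not invalidate the analysis or any stated figure.

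**What to change.** In section 6.3 and the synopsis, add baseline PCPC to the fixed covariates of the primary mixed logistic model, for example as 1-2, 3 and 4-5. State a simple rule for a missing baseline score, and say that the reported odds ratio is conditional on baseline PCPC. Make the change before the first formal efficacy assessment at 2 years (section 6.5), since adding a covariate after outcomes have been seen is open to challenge.

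Prespecify one sensitivity analysis that also adjusts for the vasoactive inotropic score in the 2 hours before CPR, with its own missing-value rule.

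The cost is a line of text in each place, one or two more parameters in the primary model, and no new data collection.
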